3.2.7 Medical and surgical history

Medical and surgical history, including ongoing medical history, as well as any significant conditions, including but not limited to major abdominal surgeries (excludes appendectomy), renal failure/dysfunction, liver failure/dysfunction, cardiac disorders inflammatory bowel disease, polyposis, diabetes, cancer (must indicate type of cancer), immune system disorders, electrolyte abnormalities will be coded using MedDRA current version at Ipsen coding department at the time of database lock.

Listings will present the SOC, PT and reported term and will be sorted by treatment group, subject, chronological start date, SOC, PT and reported term.

A frequency table of the number and percentage of subjects will be provided for all medical and surgical history by SOC and PT by treatment group and overall for the ITT population.

3.2.8 Subject compliance

A listing will be presented for drug administration for treatment preparation, residual volumes of preparation (volumes not taken by the subject) and start and stop times of intake by subject for each treatment group. In addition, information about the residual volume of water will be reported and listed for the Eziclen®/Izinova® treatment only.

Subject compliance to instructions of use is considered as a secondary endpoint and is described in section 3.2.1.2.10.

All major protocol deviations, defined prior to database freeze, will be listed by treatment group and subject. Additionally all major protocol deviations will be summarised on the ITT population and those with impact on the populations will also be described.

3.2.9 *Prior and concomitant therapies*

Medications will be coded using World Health Organization – Drug dictionary (WHO-DD) with the current version at Ipsen coding department at the time of database lock. The therapeutic class will correspond to the second level of Anatomic Therapeutic Class (ATC) code, which corresponds to the first 3 digits.

Non-drug therapies and surgical procedures will be coded using MedDRA Dictionary with the current version at Ipsen coding department at the time of database lock.

The date of first administration of study drug (study day 1) will be used as the cut-off date for the definition of prior and concomitant. A drug that started before study day 1 and is continuing at time of day 1 will be considered as both, prior and concomitant. Prior, concomitant and both prior and concomitant will be flagged P, C and PC respectively, in all listings.

Prior and concomitant medications will be listed with the therapeutic class, preferred name and reported term and they will be sorted by treatment group, subject, chronological start date, therapeutic class, preferred name and reported term.

Frequency tables of the number and percentage of subjects with at least one prior medication will be provided by therapeutic class and preferred name for the ITT population.

A similar table will be presented for concomitant medications.

Prior and concomitant non-drug therapies will be listed with the SOC, PT and reported term and they will be sorted by treatment group, subject, chronological start date, SOC, PT and reported term.

Concomitant surgical procedures will be listed with the SOC, PT and reported term and they will be sorted by treatment group, subject, chronological start date, SOC, PT and reported term.

3.2.10 Derived data

The derived data are data which are calculated according to Analysis Data Model (ADaM) standard from the raw data in the eCRF, not included in the Study Data Tabulation Model (SDTM) database, and displayed in the individual data listings. The list of derived data is displayed in Appendix 1.

3.2.11 Rules and data formats

Data will be presented using an appropriate number of decimal places (i.e. the number of decimal places used does not imply undue precision). Raw data will be presented to the number of decimal places collected, and derived data will be presented to an appropriate number of decimal places. The appropriate number of decimal places will be determined by general practice, mathematical rationale or scientific rationale (e.g. age should be presented in whole numbers).

For summary statistics, the following will be presented n, arithmetic mean, SD, median and the range (minimum, maximum).

Mean, SD and median values will be reported to one decimal place greater than the raw/derived data that they summarise. Minimum and maximum values will be reported with the same precision as the raw data.

Percentages will be reported to 1 decimal place and 0 % will not be presented. Percentages will be calculated using a denominator of all subjects in a specified population with available data. The denominator will be specified in a footnote to the tables for clarification if necessary.

All values below or above a limit of detection (e.g. < 0.1 or > 100) will be listed as such. For each parameter for which it is possible to have values below or above a limit of quantification, the rule to be used in the statistical tables is to replace values below or above a limit of quantification by the limit of quantification.

All text fields must be left justified and numeric or numeric with some text specification (e.g. not done, unknown, < 4.5, ...) must be decimal justified. Dates will be presented in the format [ddmmmyyyy] and times in the format [hh:mm].

3.2.12 Pooling of centres

It is not planned to perform subgroup analyses on individual or groups of centres but efficacy analyses will be adjusted on countries.

3.2.13 Interim analysis

No interim analysis will be performed.

3.2.14 Role of expert safety data review committee

An Expert Committee will be appointed to review safety data. This Expert Committee will be chaired by the international coordinator and be composed of the coordinators from each country involved. Two reviews will be performed during data review meeting, first when 50 subjects will be included (i.e. when 20 % of the planned number of subjects have undergone colonoscopy corresponding to Visit 2 at Day 2) and second when 125 subjects will be included (when 50 % of the subjects have reached the Visit 2 at Day 2). Blinded descriptive tables will be produced by the study statistician on enrollment and disposition by country and overall, baseline characteristics (including age, sex, medical history, concomitant medications and indication for colonoscopy) safety with description of AEs (including overall summary of AEs and frequency tables by SOC and PT on SAEs, AEs, TEAEs, related TEAEs, AE leading to withdrawal and AE leading to death) and tolerability. Additionally, supporting individual blinded data listings on lab data, AEs, and tolerability will be provided.

3.2.15 Covariates and analysis of subgroups

Descriptive statistics for primary endpoint may be provided per country, age range ([12-14[/ [14-16[/ [16-18[years), weight range (]40-50] /]50-60] / >60 kg) and sex.

Exploratory analyses will be presented by repeating the primary analysis in the mITT by age class, weight class and sex using the main model with additional term for subgroup and the interaction treatment * subgroup, as well as the treatment * country interaction if found significant in the primary analysis, as follows:

proc logistic data=ADCC(where=(PARAM='Successful overall preparation' and MITTFL='Y'));

class TRTP(ref='KLEAN-PREP') COUNTRYC(ref='Largest country') SUBGROUP(ref='Class1') / param=glm;

model AVALC(EVENT='Yes') = TRTP COUNTRYC /* TRTP*COUNTRYC
*/ SUBGROUP TRTP*SUBGROUP / link=logit lackfit firth;

lsmeans TRTP*SUBGROUP / cl;

4 COMPUTER SYSTEMS, SOFTWARE AND VALIDATION OF PROGRAMS

4.1 Hardware

The statistical analysis will be performed using a PC on a Windows 7 operating system.

4.2 Software

All tables, figures and listings (TFLs) will be produced and statistical analysis performed using SAS version 9.4 or higher [5]. All outputs will be in Microsoft Word Format.

4.3 Validation programs

Biotrial Biometrics will provide a validation plan to Ipsen identifying the methods of validation.

The study statistician is responsible for reviewing each output associated with the deliverable product. Program logs are checked by the statistical programmer for logical, syntax and fatal errors. The checks in SAS includes, but is not limited to, all ERRORS, WARNINGS, BY-VALUE merge messages, NOTES, and UNINITIALIZED variables. Program logs are also reviewed for accurate and consistent variable and observation counts following each procedure and data step.

The study statistician is responsible for checking and reviewing the work produced using double-programming for the primary endpoint and whatever method he/she feels is appropriate (e.g. SAS code review, hand calculation, etc.) to reassure of the quality of the output.

Outputs are reviewed for typographical errors, misspellings and nonsensical values or results and to check the consistency with the statistical analysis plan. Outputs are cross-checked against each other for accuracy and consistency. For statistical tables, listings, appendix listings, and figures, this procedure includes comparison of subject group numbers, counts of subjects at each observation point, and consistency of results for variables between outputs.

Findings of the quality control reviews are communicated to the party responsible for making necessary changes. The programs will be retested after modifications.

After final review, and when no further change is required to produce the deliverable, the statistical programmer and the study statistician have to complete and sign the quality control and statistical analysis results follow-up's validation checklist, to indicate that they have successfully performed all of their responsibilities. Copies of the internal QC forms produced for the validation process will be provided to the sponsor to support the validation.

4.4 **Restitution of the programs**

All programs (including macros and analysis datasets) producing the tables, listings and statistical outputs along with associated logs should be given to the sponsor when the TFLs and statistical analyses have been finalised.

5 CHANGES FROM PROTOCOL

It was planned in the protocol to tabulate the efficacy and safety (laboratory, vital signs and tolerability) results by treatment group and overall, but this is not relevant to pool them so only description by treatment group will be provided.

48/62

It was planned in the protocol to include the interaction treatment*country in the ANOVAs of the applicable secondary endpoints, but as for the primary analysis the interaction will rather be investigated and kept only if it is significant.

It was not planned in the protocol to perform secondary analyses on mITT and PP, but it was decided to take into account the significant difference in terms of number of patients between ITT and the mITT and PP populations in order to assess the robustness of the results.

It was not planned in the protocol to present the primary endpoint according to subgroups (age class, weight class and sex), but descriptive statics have been added to explore the primary results.

It was not planned in the protocol to describe the time between the last intake of fluids and the start of colonoscopy procedure, but as this factor has been shown to be a major contributor to quality in adult patients it has been decided to add this description (Hassan et al.).

It was planned in the protocol to exclude from the PP population all subjects with major deviations, but some major deviations do not have an impact on the analyses, so they have been identified in the Protocol Deviation Document and the definition of the PP population has been updated to only consider the deviations having an impact on the analyses.

6 **REFERENCES**

- 1 Schwartz GJ and Work DF. Measurement and Estimation of GFR in Children and Adolescents. Clin J Am Soc Nephrol. 2009; 4: 1832–1843
- 3 International Conference on Harmonisation (ICH) E9 and Federal register Vol. 63, No. 179 (September 1998).
- 4 SAS, Version 9.3. SAS Institute Inc., Cary, NC, USA, 2012.
- 5 Brookmeyer, R. and Crowley, J. (1982), "A Confidence Interval for the Median Survival Time" Biometrics, 38, 29–41.
- 6 Karvanen J. The statistical basis of laboratory data normalization. Drug Information Journal. 2003;37(1):101-107.

Appendix 1 Derived data

The following derived data will be calculated:

(1) Treatment group

Treatment groups will be defined as "Eziclen/Izinova" and "Klean-Prep".

(2) Study duration

Study duration (days) will be calculated as (last visit attended - date of informed consent) + 1.

- (3) Successful treatment preparation
- A successful preparation will be derived from a colon cleansing scored as excellent (4) or good (3).
- A failure preparation will be defined as:
 - Fair (2) or poor (1) according to colon cleansing score,
 - Any subject who did not have a colonoscopy based on the investigator's assessment of the cleansing (insufficient faecal output, unclear faecal discharge, etc.) or due to preparation related AEs,
 - Any subject for whom cleaning was not adequate for evaluation,
 - Any subject for whom rescue treatment (saline enema) was needed.

(4) Time to clear effluent

It is defined as the time (expressed in hours) from the first intake of prescription to the first clear watery stool occurrence if any, or to the time of colonoscope introduction, if no clear watery stool is observed before the beginning of the procedure and then the time will be considered as censored for the survival analysis. See section 3.2.1.2.3.

(5) Completion of the procedure

"Yes" if the colonoscopy reached the caecum and the item "Was physician able to reach the caecum?" is "Yes", "No" otherwise.

(6) Duration of the intubation

It is defined as the time (expressed in minutes) from colonoscope introduction to caecal intubation.

(7) Duration of the examination

It is defined as the time (expressed in minutes) from caecal intubation to colonoscope withdrawal.

(8) Need of a rescue treatment

"Yes" if a rescue medication was administered and the item "Was any enema needed to achieve preparation?" is "Yes", "No" otherwise.

(9) Need of a nasogastric tube to complete preparation

"Yes" if a nasogastric tube was inserted and the item "Was a nasogastric tube inserted?" is "Yes" at dose 1 or dose 2, "No" otherwise.

(10) Compliance in percentage

The percentage of compliance is defined as (planned volume - residual volume) / planned volume, adding up the solution and water volume where applicable.

50/62

The planned volume is 750 mL for Eziclen (375 mL per dose), 1500 mL for hydration (750 mL per dose) and 70 mL/kg for Klean-Prep® with a maximum of 4000 mL (maximum 2000 mL per dose).

(11) Compliance with the instructions of use

A subject is considered as compliant with the instructions of use if he/she drinks the whole preparation (100% of compliance) and any required further fluid intake (100% of compliance).

The planned volume is 750 mL for Eziclen (375 mL per dose), 1500 mL for hydration (750 mL per dose) and 70 mL/kg for Klean-Prep® with a maximum of 4000 mL (maximum 2000 mL per dose).

(12) Compliance in class

The compliance in class is defined from the compliance in percentage as follows:

- 100 %,
-]100-75],
-]75-50],
- < 50 %.
- (13) Lesions caused by colonic lavage

Histological examination results of lesions caused by colonic lavage will be identified among the adverse events by looking for the term "colonic lavage" in the verbatim term, since the investigator should identified the suspected lesions using "suspected to have been caused by colonic lavage". The occurrence (Yes/no) will then be derived for each subject.

(14) Baseline

Baseline will be derived as the last available assessment before administration of the IMP.

(15) Changes from baseline

Changes from baseline will be calculated as a difference from baseline (e.g. assessment at the visit – assessment at baseline).

(16) Therapeutic Class.

The therapeutic class will correspond to the first 3 digits of the ATC code. The decoding of the therapeutic class will be done from the WHO-DD (current version at the time of database lock).

(17) Prior and concomitant flags

The date of first administration of study treatment (study day 1) is used as the cut-off date for the definition of prior and concomitant medications. A drug started before study day 1 and continuing at time of Day 1 is considered as both, prior and concomitant. Prior, concomitant and both prior and concomitant will be coded as P, C and PC respectively.

(18) Concomitant therapy duration

If times are available, the duration of concomitant treatments will be calculated as (end date/time - start date/time). If at least one time is missing, the duration of concomitant treatments will be calculated as (end date - start date) + 1. If the recorded end date is continuing at the end of the study then the end date will be listed as "ongoing" and the duration will be approximated as " \geq (last attended visit date - start date) + 1" day(s). If the start date or the end date are partial, the duration will be presented as an inequality " \geq xx" day(s) [i.e. \geq 2 where start date=31JAN2004 and end date=FEB2004 or start date=JAN2004

51/62

and end date=01FEB2004] but if both are partial or one is missing the duration will not be presented.

(19) Adverse event duration

If the start and end dates of the adverse event are identical then "<1" day will be presented with the duration in hh:mm recorded in the eCRF if it is available. If times are available, the duration will be calculated as (end date/time – start date/time) and presented in days hh:mm. If at least one time is missing and if the duration is greater than 24 hours then it will be calculated as (end date - start date) + 1 and presented in days. If the recorded end date is continuing at the end of the study, the end date will be listed as "ongoing" and the duration will be approximated as " \geq (last attended visit date – start date) + 1" day(s). If the start date or the end date are partial the duration will be presented as a superior inequality " \geq xx" day(s) [i.e. \geq 2 where start date=31JAN2004 and end date=FEB2004 or start date=JAN2004 and end date=01FEB2004].

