1.4.2 Subjects assessments

1.4.2.1 Efficacy assessments

Blinded overall assessment of preparation efficacy will be determined by the colonoscopist upon completion of the examination, based on a 4-point scale. The colonoscopist will score the quality of the bowel preparation using the following Cleansing Score (Table 1).

Score	Grade	Description
4	Excellent	No more than small bits of adherent faeces/fluid
3	Good	Small amounts of faeces or fluid not interfering with examination
2	Fair	Enough faeces or fluid to prevent a completely reliable examination
1	Poor	Large amounts of faecal residue, additional cleansing required

Table 1Cleansing Score

The primary efficacy will be assessed on the basis of preparation success or failure. The primary efficacy variable is the proportion of subjects with a successful overall preparation.

Only perfect preparations graded as excellent (4) or good (3), which allow full, reliable examination of the mucosa, will be considered as successful.

The secondary efficacy endpoints are summarised below (Table 2):

Endpoint	Timepoint	Evaluation
Colon cleansing	V2 (Colonoscopy)	Cleansing Score assessed on 4 levels (4-point scale, see Table 1).
Overall and segmental cleansing assessed by Boston Bowel Preparation Scale (BBPS)	V2 (Colonoscopy)	BBPS (see Table 3) Overall score [1]. Segmental scores (left colon (LC), transverse colon (TC), right colon (RC)).
Time to clear effluent (hours)	V1 (Treatment)	Time between first intake of prescription and first clear watery stool.
Complete procedure	V2 (Colonoscopy)	Number (%) of complete procedures defined as procedures that reached the caecum.
Time to caecal intubation (minutes)	V2 (Colonoscopy)	Time between the colonoscope introduction and the time to reach caecum.
Duration of examination (minutes)	V2 (Colonoscopy)	Time between the caecum is reached and the withdrawal of the colonoscope.
Need for rescue treatment because of inadequate preparation intake.	V2 (before colonoscopy)	Number (%) of procedures that need a rescue treatment (saline enema).
Treatment acceptability	V1 (Treatment)	Level of acceptability of treatment assessed using a 5- point Treatment Acceptability Questionnaire (see Table 4).
Need for nasogastric tube	V1 (Treatment)	Number (%) of subjects who need a nasogastric tube to complete preparation.
Treatment compliance	V1 (Treatment)	Percentage of volume of fluid taken relative to the planned volume of fluid to be taken

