3.2.1.2.4 Complete procedure

The proportion of complete procedure (defined as procedures (i.e. colonoscopies) that reached the caecum) will be assessed. It will be tabulated by treatment group using frequency count with two-sided 95 % CI and analysed using Cochran-Mantel-Hænszel (CMH) chi-square for the proportions adjusting for country effect. The general association statistic will be used to assess the test significance.

The SAS Freq procedure will be used as follows:

proc freq data=ADPR(where=(PRTRT='COLONOSCOPY' and AVISITN=2 and ITTFL='Y'));

```
table COUNTRYC*TRTP*PROCCUR / CMH;
```

run;

The difference of proportions with the 95 % CI and p-value will be summarised.

The reasons for non-completion will also be presented.

3.2.1.2.5 *Time to caecal intubation*

The time to caecal intubation (from colonoscope introduction to caecal intubation) will be assessed and will be analysed using survival methods on subjects who performed colonoscopy.

Table 8 specifies the event and censoring dates to be used in the analysis of time to clear effluent.

	· · · · ·	
Event	Time of event	Outcome
Caecal intubation	Time of caecal intubation	Event
Procedure (i.e. colonoscopy) did not reach the caecum	Time of withdrawal of colonoscope	Censored

Table 8Time to caecal intubation (minutes)

The distribution of time to caecal intubation will be estimated using the Kaplan-Meier (KM) product limit method. The results will be presented in a summary table and a KM plot will also be constructed.

The summary table will present by treatment group the numbers and percentages of subjects with occurrence of caecal intubation and the numbers and percentages of censored subjects. The summary will also include the median time to caecal intubation as well as the 25th and 75th percentiles with their two-sided 95 % CI, the percentage and 95 % CIs of subjects who had caecal intubation at 5, 10, 15, 20, 25, 30, 45 and 60 minutes from KM estimates.

Confidence intervals for median time to caecal intubation as well as the 25th and 75th percentile CIs will be calculated using the method of Brookmeyer and Crowley (1982) [5], which is the default method within SAS® version 9 and higher.

Kaplan-Meier curves will be constructed by treatment group and will display the number of subjects at risk at 5, 10, 15, 20, 25, 30, 45 and 60 minutes.

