3.2.1.2.7 Rescue treatment

The proportion of procedures that need a rescue treatment (saline enema) because of inadequate preparation intake will be assessed. It will be tabulated by treatment group using frequency count with two-sided 95 % CI and analysed using Cochran-Mantel-Hænszel (CMH) chi-square for the proportions adjusting for country effect. The general association statistic will be used to assess the test significance.

The SAS Freq procedure will be used as follows:

```
proc freq data=ADCM(where=(CMCAT='RESCUE MEDICATION' and CMTRT='ENEMA' and ITTFL='Y'));
table COUNTRYC*TRTP*CMOCCUR / CMH;
```

run;

The difference of proportions with the 95 % CI and p-value will be summarised.

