3.2.3 Missing data and outliers

3.2.3.1 Missing data

No missing value will be replaced, except for the primary analysis where the missing preparation evaluations (because of colonoscopy not done because of inadequate preparation or preparation-related AEs) will be considered as failures.

In the description of qualitative parameters, subjects with a value counted as "missing" at a visit will be identified as subjects being not assessed.

If a value required a retest, the last reliable non-missing value will be taken into account if measured before the first intake of treatment; and the first non-missing reliable value for postbaseline assessments. An assessment will be considered reliable if it is performed without any technical problem and if the result is within the range of plausible values. Any retest or unscheduled assessments performed will be included in the individual subject data listings.

If there is a significant number of missing values for a subject (or if there is confirmed data appearing spurious), a decision will be made following consultation with the sponsor regarding the handling of these data in summaries, prior to database freeze.

Any repeat or additional assessments performed will be included in the individual subject data listings.

3.2.3.2 *Missing or incomplete dates*

In all listings, missing or incomplete dates should be left as they have been recorded. However, for calculation / sorting / assignation based on dates, the following methods will be used:

- The most conservative approach will be systematically considered (i.e. if the onset date of an AE/concomitant medication is missing / incomplete, it is assumed to have occurred during the study treatment phase (i.e. a TEAE for AEs) except if the partial onset date or other data [stop date, ...] indicates differently).
- A missing/incomplete date of medical history or disease diagnosis will be assumed to have occurred before any study treatment.
- If a partial date and the associated information do not allow to state about the assignation to a group / category, all the possible groups / categories will be considered (e.g. a medication with partial start and stop dates could be considered as prior and concomitant treatment).

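### SAP Appendix 1 turns unanswered caecum, enema and tube items into No, and can count a subject without a colonoscopy as an incomplete procedure, against the SAP's own missing-data and denominator rules

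*SAP*

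**What the plan says.** Three binary endpoints are derived in SAP Appendix 1 by the same pattern:

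- Item 5, completion: "Yes' if the colonoscopy reached the caecum and the item 'Was physician able to reach the caecum?' is 'Yes', 'No' otherwise".
- Item 8, rescue: "Yes' if a rescue medication was administered and the item 'Was any enema needed to achieve preparation?' is 'Yes', 'No' otherwise".
- Item 9, nasogastric tube: the value depends on whether the insertion item "is 'Yes' at dose 1 or dose 2, 'No' otherwise".

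None of the three has a missing or not-applicable level.

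The endpoints are defined in the body of the SAP:

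- Completion (3.2.1.2.4): "The proportion of complete procedure (defined as procedures (i.e. colonoscopies) that reached the caecum) will be assessed".
- Rescue (3.2.1.2.7): "The proportion of procedures that need a rescue treatment (saline enema) because of inadequate preparation intake will be assessed". Table 2 in 1.4.2.1 places the assessment at Visit 2, before colonoscopy.
- Tube (1.4.2.1, Table 2): "Number (%) of subjects who need a nasogastric tube to complete preparation", at Visit 1.

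All three are analysed on ITT (3.2.1.2), which is every randomised subject who took any study drug, with or without a colonoscopy (2.1.1). Two general rules also apply. SAP 3.2.3.1 states: "No missing value will be replaced, except for the primary analysis where the missing preparation evaluations" (those left unevaluated for a preparation-related reason) count as failures. SAP 3.2.11 states: "Percentages will be calculated using a denominator of all subjects in a specified population with available data".

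**The concern.** A derivation that sends everything except a documented Yes to No does two things that the rest of the SAP does not intend.

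First, it fills in blanks. An unanswered caecum, enema or tube item becomes a definite No and enters the denominator. It also disables a safeguard: SAP 3.2 asks for the number of missing values for categorical variables, and under this coding that number is always zero for these three. Items 5 and 8 join two conditions, so, read literally, an enema that was given but whose eCRF question is blank is also coded No.

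Second, for completion it can merge two different outcomes: a colonoscope that did not reach the caecum, and a colonoscopy that never took place. The SAP writes the restriction out for neighbouring endpoints. Time to caecal intubation (3.2.1.2.5) is limited to subjects who had the colonoscopy, and duration of examination (3.2.1.2.6) leaves out those whose caecum was not reached. Completion has no such sentence.

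At stake are three secondary efficacy endpoints. Completion also bears on the objective of comparing colonoscopy quality indicators (SAP 1.2.2). Each is reported with a difference in proportions, a 95% CI and a p-value.

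**Working it through.** **Arm size.** The plan's own figure is used only to set the scale. Inputs from Protocol 10.2 and SAP 1.4.4: 85% success in both arms, margin 15%, one-sided alpha 0.025, power 90%. The unpooled normal approximation gives n = (1.960 + 1.282)² × 2 × 0.85 × 0.15 / 0.15² ≈ 119.1, so 120 per arm. With 4% loss, 120 / 0.96 = 125. Both figures reproduce.

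**Effect of the coding on one arm.** Let N be the ITT subjects in the arm, m those with no valid answer (a blank item or, for completion, possibly no colonoscopy), and x the number coded Yes.

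- Rate on available data: x / (N − m).
- Rate under Appendix 1: x / N = [x / (N − m)] × (1 − m/N).

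Every rate is multiplied by a factor below 1, so all three fall. A lower completion rate is unfavourable; lower rescue and tube rates are favourable.

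**Numbers.** N = 125 assumes that all randomised subjects were dosed. The documents give no rates for these endpoints, so 95% (completion), 10% (rescue) and 20% (tube) are assumptions, as are the values of m. The middle row borrows the plan's 4% only as a scale (5 of 125); in the plan that figure is dropout and non-compliance, not missing items or cancelled colonoscopies.

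| m | Completion | Rescue | Tube |
|---|---|---|---|
| 2 | 117/123 = 95.1% → 117/125 = 93.6% (−1.5) | 12/123 = 9.8% → 12/125 = 9.6% (−0.2) | 25/123 = 20.3% → 25/125 = 20.0% (−0.3) |
| 5 | 114/120 = 95.0% → 114/125 = 91.2% (−3.8) | 12/120 = 10.0% → 12/125 = 9.6% (−0.4) | 24/120 = 20.0% → 24/125 = 19.2% (−0.8) |
| 10 | 109/115 = 94.8% → 109/125 = 87.2% (−7.6) | 12/115 = 10.4% → 12/125 = 9.6% (−0.8) | 23/115 = 20.0% → 23/125 = 18.4% (−1.6) |

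**Effect on the arm difference.** With equal true rates p and affected numbers mA and mB, the spurious difference is p × (mB − mA) / N.

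- 5 versus 5 affected: zero for all three.
- 2 versus 8: 0.95 × 6/125 = 4.6 points for completion, 0.10 × 6/125 = 0.5 for rescue, 0.20 × 6/125 = 1.0 for tube.
- 0 versus 10: 7.6, 0.8 and 1.6 points.

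A material false difference therefore needs clearly unequal numbers of affected subjects, and in practice concerns completion.

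**The case against.** The strongest reply has five parts.

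1. **No on ITT is a legitimate definition of completion.** The secondary endpoint list (SAP 3.1.2) describes a procedure documented as completed, and a subject with no colonoscopy has none. It also parallels the primary rule that a colonoscopy cancelled for preparation reasons is a failure. This stands to the extent that the ITT version is worth showing. It does not remove the conflict with 3.2.1.2.4, which makes the colonoscopy the unit.

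2. **Much of the disclosure is already planned.** Reasons for non-completion (3.2.1.2.4), a flow chart with colonoscopies performed and completed (3.2.4) and counts by arm (3.2.5) let a reader recover most of the per-colonoscopy rate. This stands and lowers the severity. It does not recover blank enema or tube items.

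3. **The denominator is not established.** A reader might infer that subjects without a colonoscopy are certain to enter the completion rate. The code in 3.2.1.2.4 filters colonoscopy records at Visit 2, and 3.2.1.2.7 filters enema records. The documents do not show whether such subjects have a record there. This stands: the effect is possible, not certain.

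4. **A missing colonoscopy does not by itself distort rescue or tube need.** An enema or tube recorded as Yes stays Yes, and a subject cancelled without an enema may have a true No. Tube need is counted per subject at Visit 1, so a reader who infers that its endpoint definition is contradicted goes too far; its only conflict is with 3.2.3.1 and 3.2.11. Rescue is worded per procedure but analysed on ITT, a looser mismatch.

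5. **The primary endpoint need not be touched.** Need for rescue is a primary failure criterion, so a reader might infer that a blank enema item with a score of 3 or 4 is counted as a success. No text says that the primary derivation uses item 8. Rescue need must be recorded in the eCRF (Protocol 3.4), missing data are queried (Protocol 14.2.1), and the primary endpoint is double-programmed (SAP 4.3). The link is only conditional.

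**Conclusion.** The point holds, as a minor one. For all three items, coding an unanswered question as No contradicts SAP 3.2.3.1 and 3.2.11. For completion, a dosed subject without a colonoscopy can also be coded No, which does not fit the definition in 3.2.1.2.4.

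The direction is the same throughout: the rates fall. A reader might infer from the mixed favourability that they move in opposite directions; they do not. A reader might also infer a bias towards one preparation, but the documents give no counts by arm, and equal numbers of affected subjects with equal true rates produce no false difference.

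The sizes above rest wholly on assumed rates and assumed counts. Completion is the only endpoint where a handful of affected subjects shifts the rate by several points. All three endpoints are tested for description only (SAP 3.1.5), so the non-inferiority conclusion is not affected unless item 8 feeds the primary failure rule, which the SAP neither states nor excludes.

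**What to change.** - **Items 5, 8 and 9:** code No only when the eCRF item is answered No, and leave an unanswered item missing so that it appears in the missing count. For item 9, No means answered No for each dose given.
- **Completion (item 5):** compute it among subjects who had a colonoscopy, as 3.2.1.2.4 defines it. Add the ITT version, with no colonoscopy counted as not completed, as a supportive row.
- **Rescue (item 8) and tube need (item 9):** keep them on all ITT subjects with an answered item. Do not restrict rescue to subjects who had a colonoscopy: that would drop those who received an enema and were still cancelled, who are among the clearest preparation failures.
- **Primary endpoint:** if item 8 feeds the failure rule, state that a blank enema item is not read as no rescue.

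The cost is a few lines of SAP text, one derivation line per item and one extra table row. No new data are needed.
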